### 6.2.1. Dose Delays in Treatment Period

In case of dose delay (refer to Table 5), the clinical assessments and procedures to be performed include but are not limited to:

- All planned Day 1 assessments should be performed and appropriate samples sent to the central laboratory, regardless of the dose delay.
- If dose delay is due to **an AE, a laboratory or vital signs abnormality** (refer to Table 5, Dose Delay, Dose Reduction and Discontinuation Guidelines, Section 7.2.1.2), repeat any clinically indicated assessment by local laboratory at a frequency decided by the Investigator until the subject meets either the treatment administration criteria or treatment discontinuation criteria, as detailed in Section 7.2 and Section 11.1.
- If dose delay is **due to increased hemoglobin level** (refer to Table 5, Dose Delay, Dose Reduction and Discontinuation Guidelines, Section 7.2.1.2), perform hematology on Day 1 of dose delay by central laboratory and then at least weekly by local lab, until the subject meets either the treatment administration criteria or treatment discontinuation criteria, as detailed in Section 7.2 and Section 11.1
- PK/ADA samples should be performed on Day 1 of dose delay and before next dose.
- At the time of IP administration following a dose delay, perform the scheduled dosing visit assessments (laboratory assessments should be performed by central laboratory) as detailed in the Table of Events, Table 3, and Section 6.2, regardless of the duration of the dose delay.

### 6.3. Long-term Treatment Period

All subjects, whether randomized to luspatercept or placebo, who complete the double-blind treatment period of this study will have the opportunity to enroll in the Long-term Treatment Period and continue to receive IP to which subjects have been initially assigned, as described in Section 3.1.3. An administrative visit window of  $\pm 5$  days is permitted.

During the Long-term Treatment Period all laboratory assessments should be measured by central laboratory. Data are to be entered in the eCRF.

The assessments and procedures that will be performed during the Long-term Treatment Period are outlined in the Table of Events (see [Table 3](#)) and include but are not limited to:

- Iron chelating therapies: record on an ongoing basis (as detailed in [Section 6.1](#)).
- Other concomitant medications/therapies: such as surgery, radiation, systemic or any other therapy for the subject's disease - record on an ongoing basis.
- Concomitant procedures - record on an ongoing basis.
- Transfusion assessment - record on an ongoing basis (as detailed in [Section 6.1](#)). In addition, as detailed in [Section 6.1](#), a subject diary will be available (refer to [Section 6.1](#))
- Adverse event assessment - record on an ongoing basis (refer to [Section 6.1](#) and [Section 10](#) for additional information).
- Malignancy and Pre-Malignancy Reporting (refer to [Section 6.1](#) and [Section 10.5.2](#) for additional information)
- Vital signs (as detailed in [Section 6.1](#))
- Weight
- Cardiac Doppler echocardiography, MUGA or MRI - left ventricular ejection fraction (LVEF)
- Urine or serum medically supervised pregnancy test with a minimum sensitivity of 25 mIU/mL for FCBP at Day 1 of each dose schedule.
- For female subjects – menstrual status
- Hematology (as detailed in [Section 6.1](#))
- Serum chemistry (as detailed in [Section 6.1](#))
- Urinalysis: microalbumin, creatinine, microalbumin/creatinine ratio (morning void; central lab)
- PK and ADA (if applicable) – refer to [Sections 6.8](#) and [6.9](#)
- Serum ferritin
- MRI for LIC (T2\* or R2, mg/g dw). The same MRI technique should be used within a subject throughout the study duration.
- MRI or abdominal ultrasound for spleen measurement, unless splenectomized (as detailed in [Section 6.1](#)).
- MRI for myocardial iron (T2\*; ms)
- Bone mineral density of total hip and lumbar spine by DXA scan (as detailed in [Section 6.1](#))

- QoL self-administered questionnaire TranQoL; SF36
- HRU
- Administration / Accountability of luspatercept on Day 1 of each dose

### 6.3.1. Dose Delays in Long-term Treatment Period

In case of dose delay (refer to [Table 5](#)), the clinical assessments and procedures to be performed include but are not limited to:

- All planned Day 1 assessments should be performed regardless of the dose delay.
- If dose delay is due to **an AE, a laboratory or vital signs abnormality** (refer to [Table 5](#), Dose Delay, Dose Reduction and Discontinuation Guidelines, Section 7.2.1.2), repeat any clinically indicated assessment by local laboratory at a frequency decided by the Investigator until the subject meets either the treatment administration criteria or treatment discontinuation criteria, as detailed in Section 7.2 and Section 11.1.
- If dose delay is **due to increased hemoglobin level** (refer to [Table 5](#), Dose Delay, Dose Reduction and Discontinuation Guidelines, Section 7.2.1.2), perform hematology on Day 1 of dose delay by central laboratory and then at least weekly by local lab until the subject meets either the treatment administration criteria or treatment discontinuation criteria, as detailed in Section 7.2 and Section 11.1.
- At the time of IP administration following a dose delay, perform the scheduled dosing visit assessments (laboratory assessments should be performed by central laboratory) as detailed in the Table of Events, [Table 3](#), and Section 6.3, regardless of the duration of the dose delay.

### 6.4. Open-label Phase

During the Open-label Phase, the following evaluations will be performed at the frequency specified in the Table of Events, [Table 3](#). The evaluations should be performed prior to dosing on the visit day, as applicable, unless otherwise specified. An administrative visit window of  $\pm 5$  days is permitted.

**Only subjects who, at the time of unblinding, are in Post-treatment Follow-Up and are on placebo, will perform the following assessments and procedures in addition to the procedures and assessments that will be performed by subjects who are continuing the treatment with luspatercept after the unblinding of the study:**

- Assessment of eligibility (only subjects who are in the Post-treatment Follow-up who were treated with placebo during the double-blind treatment and discontinued the IP). Inclusion criteria numbers 6 and 7 and exclusion criteria numbers 1-10, 15-17 and 21 must be met at Dose 1 Day 1
- Iron chelating therapies: including type of iron chelating therapy, period of treatment (ie, dates) and dose changes 24 weeks prior to Dose 1 Day 1 with luspatercept in the Open label Phase and record on ongoing basis (as detailed in Section 6.1).

- Prior medications/therapies: 24 weeks prior to Dose 1 Day 1 of luspatercept
- Prior procedures 24 weeks prior to Dose 1 Day 1 of luspatercept
- Transfusion assessment – 24 weeks RBC transfusion history prior to Dose 1 Day 1 of the Open-label Phase of luspatercept including Hb levels prior to each transfusion, the number of units and or volumes transfused, and the dates of transfusion. If available, the Hct of the transfused unit should be collected, as well as the age when the subject started regular transfusion. These retrospective data will be recorded in the subject's electronic case report form (eCRF).
- Serum ferritin: 24 weeks prior to Dose 1 Day 1 of luspatercept.
- ECOG performance status ([Appendix B](#))
- 12-Lead Electrocardiogram – read locally
- Females: Serum medically supervised pregnancy test with a minimum sensitivity of 25 mIU/mL for FCBP at Day 1 Dose 1 of luspatercept
- Serum chemistry (as detailed in [Section 6.1](#))
- Urinalysis: microalbumin, creatinine, microalbumin/creatinine (as detailed in [Section 6.1](#))

**All subjects**, ie, subjects who are continuing the treatment with luspatercept after the unblinding of the study, and subjects who are starting the treatment with luspatercept after received placebo in the double-blind treatment, will perform the following assessments and procedures:

- Iron chelating therapies: record on an ongoing basis (as detailed in [Section 6.1](#)).
- Concomitant medications/therapies: such as surgery, radiation, systemic or any other therapy for the subject's disease - record on ongoing basis.
- Concomitant procedures - record on ongoing basis.
- Transfusion assessment - record on an ongoing basis (as detailed in [Section 6.1](#)). In addition, as detailed in [Section 6.1](#), a subject diary will be available (refer to [Section 6.1](#))
- Adverse event assessment - record on an ongoing basis as detailed in [Section 6.1](#) and [Section 10](#).
- Malignancy and Pre-Malignancy Reporting (refer to [Section 6.1](#) and [Section 10.5.2](#) for additional information)
- Vital signs (as detailed in [Section 6.1](#))
- Weight
- Female subjects of childbearing potential: Urine or serum medically supervised pregnancy test with a minimum sensitivity of 25 mIU/mL for FCBP at Day 1 of each dose
- Female subjects of childbearing potential: menstrual status
- Hematology (as detailed in [Section 6.1](#))
- ADA (if applicable) – refer to [Section 6.9](#) and [Table 3](#)

- HRU
- Administration of luspatercept on Day 1 of each dose
- Only at Week 96 post first dose, if applicable, ie, for subjects who entered Open-label Phase prior to reaching Week 96 in the Long-term Treatment Period:
  - MRI for LIC (mg/g dw) (as detailed in Section 6.1) - only at week 96 post first dose, if applicable.
  - MRI for myocardial iron (T2\*; ms) - only at week 96 post first dose, if applicable.
  - MRI or abdominal ultrasound for spleen measurement (as detailed in Section 6.1) - only at week 96 post first dose, if applicable.
  - Bone imaging DXA scan (as detailed in Section 6.1) - only at week 96 post first dose, if applicable.

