##### Subjects initially assigned to placebo:

- can enter the Open-label Phase only if the DMC allows it, as outlined above.
- can enter the Open-label Phase even if they have discontinued the double-blind phase, but were compliant with the protocol 48 weeks post Dose 1 Day 1, and continue their participation in the Post-treatment Follow-up Period until the time of unblinding. can stay in the Open-label Phase until all subjects initially assigned to luspatercept complete the total treatment duration of 5 years from subjects' Dose 1 Day 1 in the treatment period of this ACE-536-B-THAL-001 study or discontinue earlier.
- at the time of unblinding, placebo subjects who discontinued treatment and continued their participation in the Post-treatment Follow-up Period until the time of unblinding

will have the opportunity to enter the Open-label Phase, if they still fulfill the following main eligibility criteria, prior to receiving their first dose of luspatercept:

- Inclusion criteria: numbers 6 and 8 (Refer to Section 4.2);
- Exclusion criteria: numbers “1-10, 15-17 and 21” (Refer to Section 4.3)

Per Investigator’s request, subjects who discontinue luspatercept in the double-blind Treatment Period for reasons not related to subject’s safety, and are still in the Post-treatment Follow-up Period at the time of unblinding, may access the Open-label Phase and be re-treated with luspatercept after consultation with Sponsor Medical Monitor and review of safety and efficacy data as long as they still fulfill the above eligibility criteria prior to Dose 1 Day 1.

**Note:** Subjects who discontinue from the study before the unblinding and without completing the PTFP period are not allowed to re-enter this study and access luspatercept in the Open-label Phase.

Subjects will be discontinued from study as appropriate, for reasons listed in Section 11.

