 Vital signs (including heart rate, seated blood pressure [DBP and SBP], and temperature) will be measured at Screening, on Days 1 of each dose prior to administration of IP, at Treatment Discontinuation, at each visit during post-treatment Follow-Up, and at End of Study. Seated blood pressure should be confirmed by two separate measurements obtained predose and 10 minutes apart. The Investigator should report any clinically significant abnormal findings as adverse events.

 Pregnancy test is required for all female subjects of childbearing potential. Serum beta human chorionic gonadotropin (β-hCG pregnancy test (which must be negative) with a minimum sensitivity of 25 mIU/mL will be performed within 4 weeks prior Dose 1 Day 1. Urine (or serum) pregnancy test will be performed to assess subject eligibility within 72 hours prior to the first administration of IP, if the initial serum pregnancy test did not already occur with 72 hours of dosing (negative results required for IP administration). During the Treatment period urine or serum pregnancy test is allowed.

-  Hematology assessment includes RBC count, Hb, Hct, MCV, MCH, MCHC, RDW, WBC count with differential, absolute neutrophil count (ANC) and absolute lymphocytes, platelet and reticulocyte absolute values, and circulating erythroblast (nucleated RBC) counts. On dosing days, hemoglobin levels should be measured prior to dosing with IP to ensure Hb levels are within the acceptable ranges to allow luspatercept administration as per Section 7.2 and that luspatercept dose modification rules are followed as outlined in Table 5. Laboratory evaluations may be repeated more frequently if clinically indicated.
-  Serum chemistry (calcium, magnesium, phosphorus, blood urea nitrogen [BUN], creatinine, creatinine clearance, albumin, total protein, alkaline phosphatase, bilirubin [total, non-conjugated], AST/SGOT, ALT/SGPT, LDH and uric acid). If clinically significant, any or all laboratory evaluations should be reported as AEs and repeated more frequently, if clinically indicated.
-  For ADA test, additional blood draws are not needed. The test will be performed using the serum collected for PK samples. If ADA test is positive at the time of End of Study, the subject may need to return for additional ADA testing.
-  DXA scan of the lumbar spine and total hip for bone mineral density (BMD).

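### Protocol Sections 3.1.4 and 6.4 name different inclusion criteria for open-label entry, and no section names the women's contraception criterion for re-treated luspatercept subjects

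*Protocol*

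**What the plan says.** Two places in the protocol set entry criteria for placebo subjects who discontinued, stayed in follow-up until unblinding, and then start luspatercept. Section 3.1.4 lists "Inclusion criteria: numbers 6 and 8 (Refer to Section 4.2". Section 6.4 states "Inclusion criteria numbers 6 and 7 and exclusion criteria numbers 1-10, 15-17 and 21 must be met at Dose 1 Day 1". The exclusion criteria are the same in both: 1 to 10, 15 to 17, and 21.

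Section 3.1.4 also lets subjects who stopped luspatercept for reasons unrelated to safety be re-treated at the investigator's request. This may happen "after consultation with Sponsor Medical Monitor and review of safety and efficacy data", and "as long as they still fulfill the above eligibility criteria prior to Dose 1 Day 1". Section 6.4 has no matching check for them, because its eligibility assessment covers "only subjects who are in the Post-treatment Follow-up who were treated with placebo during the double-blind treatment and discontinued the IP".

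On pregnancy testing, Section 6.4 asks former placebo subjects for a "Serum medically supervised pregnancy test with a minimum sensitivity of 25 mIU/mL for FCBP at Day 1 Dose 1 of luspatercept", and its all-subjects list adds a "Urine or serum medically supervised pregnancy test with a minimum sensitivity of 25 mIU/mL for FCBP at Day 1 of each dose".

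**The concern.** Criteria 7 and 8 are the sex-specific contraception criteria. A site working from Section 3.1.4 has no instruction to re-apply the women's criterion. A site working from Section 6.4 has none to re-apply the men's. For re-treated luspatercept women no section supplies criterion 7.

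What is at stake is criterion 7b: true abstinence, or effective contraception starting 28 days before investigational product. Section 1.2.1.4 does not exclude teratogenicity in humans. A negative test on the dosing day shows pregnancy status on that day; it does not show that contraception or abstinence was in place beforehand. Re-entrants may have been off drug for much longer than the 12 weeks after stopping that criterion 7b covers, so the commitment made at original entry cannot be assumed to be still in force.

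**Working it through.** The protocol gives no figure to reproduce here, so the check is a comparison of lists followed by a short look at timing.

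**Inputs.** From Section 4.2: criterion 6 is ECOG 0 or 1; criterion 7 covers women of childbearing potential (tests and contraception); criterion 8 covers men. The Section 3.1.4 list is {6, 8}; the Section 6.4 list is {6, 7}. The re-treatment sentence in Section 3.1.4 points back to that section's own list. In Table 3, the open-label eligibility mark sits in a column that footnote 18 defines for discontinued placebo subjects, with a reference to Section 3.1.4.

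**Coverage by group.**

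| Group | Lists that apply | Criterion 6 | Criterion 7 | Criterion 8 |
|---|---|---|---|---|
| Discontinued placebo | 3.1.4 and 6.4 | 2 of 2 | 1 of 2 | 1 of 2 |
| Re-treated luspatercept | 3.1.4 only | 1 of 1 | 0 of 1 | 1 of 1 |

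**What still protects against dosing a pregnant woman.**

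- Exclusion 15 (pregnant or lactating) is in both lists and reaches re-treated women through Section 3.1.4.
- Testing at each open-label dose is listed for all subjects, although the clause defining that group names only continuing luspatercept subjects and former placebo subjects.
- Placebo re-entrants have the serum test at Dose 1. No second test is lost, because Table 3 footnote 2 asks for a further test only "if the initial serum pregnancy test did not already occur with 72 hours of dosing (negative results required for IP administration".
- Section 10.4.1 advises women to avoid pregnancy during the study.

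These address pregnancy status or give general advice. None confirms criterion 7b.

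**Timing.** Follow-up visits after the last dose are at Weeks 9, 24, 48, 72, 96, 120, 144 and 156 (Table 3, footnote 23). The gaps are 24 − 9 = 15 weeks, then 24 weeks each up to Week 144, then 156 − 144 = 12 weeks. The lead-in is 28 / 7 = 4 weeks, shorter than every gap, so it can lie wholly between two visits. Week 9 is the last follow-up visit with a scheduled pregnancy test (Table 3; Section 6.6), and later visits list no contraception review. The entry check is therefore where the lead-in would be confirmed. These figures describe coverage and timing; they are not a risk estimate.

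**The case against.** The strongest reply is that the two lists are not mutually exclusive. Section 3.1.4 calls its items the main criteria, and neither list claims to be complete. A site that follows both sections applies 6, 7 and 8. Footnote 18 does not tell anyone to disregard Section 6.4, which binds placebo women in plain terms. Section 1.2.1.4 separately forbids giving luspatercept to a woman who is pregnant or intends to become so. Re-treatment is exceptional and passes through the Medical Monitor. Criterion 7b speaks of starting investigational product, which re-treated women have already done, so a second lead-in is an interpretation. The visit gaps do not prove the inconsistency, and the fix adds no visit 28 days before dosing. Finally, entry is tied to unblinding, which the SAP (Section 4.1) reports as past.

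Much of this stands as a limit on size. Placebo women are covered wherever Section 6.4 is followed, the remaining risk is narrow, and the prospective value of an amendment is uncertain. It does not remove the defect. Both sections are operative text and give different lists for the same subjects. The word main does not tell a site which further criteria apply. Section 3.1.4 itself requires its criteria to be met again before the first open-label dose, so a renewed lead-in is a fair reading. None of the safeguards cited verifies contraception or abstinence before dosing.

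**Conclusion.** The inconsistency is real and minor. Criterion 7 is missing from one of the two lists for placebo women and from the only list for re-treated luspatercept women. Criterion 8 is missing from one of the two lists for placebo men. The practical gap is the explicit re-check of the contraception or abstinence lead-in; pregnancy exclusion remains in place. It concerns re-treated luspatercept women, and placebo women at any site that relied on Section 3.1.4 alone.

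The documents do not give the number of subjects affected; it is probably small. No endpoint, power or type 1 error is involved. The conclusion assumes that the 28-day lead-in is meant to apply afresh before the first open-label dose.

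**What to change.** List inclusion criteria 6, 7 and 8 in both Section 3.1.4 and Section 6.4. State that the list applies to placebo re-entrants and to re-treated luspatercept discontinuers, and extend the Section 6.4 assessment and the Table 3 eligibility column to the second group. Say explicitly that the 28-day lead-in in criterion 7b runs from the first open-label dose. Notify sites.

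For women who have already re-entered, document whether criterion 7 was confirmed before that dose. Criterion 7b already requires abstinence reviews to be source documented, which should make part of this feasible.

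The cost is a small protocol amendment with IRB/EC submission as applicable under Section 13.5, a site memo, and a short retrospective check. Since unblinding has occurred, much of the benefit lies in that check.

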#### 6.4.1. Dose Delays in Open-label Treatment Period

In case of dose delay (refer to Table 5), the clinical assessments and procedures to be performed include but are not limited to:

- If dose delay is **due to increased hemoglobin level** (refer to Table 5, Dose Delay, Dose Reduction and Discontinuation Guidelines, Section 7.2.1.2), perform hematology on Day 1 of dose delay by central laboratory and then at least weekly by local laboratory until the subject meets either the treatment administration criteria or treatment discontinuation criteria, as detailed in Sections 7.2.1.2, 7.2.1.3 and 11.1
- If dose delay is **due to an AE, laboratory or vital signs abnormality** (refer to Table 5, Dose Delay, Dose Reduction and Discontinuation Guidelines, Section 7.2.1.2), repeat any clinically indicated assessment by local laboratory at a frequency decided by the Investigator until the subject meets either the treatment administration criteria or treatment discontinuation criteria, as detailed in Sections 7.2.1.3 and 11.1

#### 6.5. Treatment Discontinuation

Reasons for treatment discontinuation are provided in Section 11. An end of treatment evaluation will be performed for subjects who are withdrawn from treatment for any reason as soon as possible after the decision to permanently discontinue treatment has been made.

Subjects who discontinue early from treatment will proceed to the Treatment Discontinuation visit within 22 days of the last dose of study drug, or, soon after the decision to discontinue the study drug, if this occurred more than 22 days after the last dose of study drug.

The assessments and procedures that will be performed at Treatment Discontinuation are outlined in the Table of Events (see Table 3) and include but are not limited to:

- Iron chelating therapies: record on an ongoing basis (as detailed in Section 6.1).
- Other concomitant medications/therapies: such as surgery, radiation, systemic or any other therapy for the subject's disease - record on an ongoing basis.

- Concomitant procedures - record on an ongoing basis.
- Transfusion assessment - record on an ongoing basis (as detailed in Section 6.1). In addition, as detailed in Section 6.1, a subject diary will be available (refer to Section 6.1)
- Adverse event assessment - record on an ongoing basis (refer to Section 6.1 and Section 10 for additional information).
- Malignancy and Pre-Malignancy Reporting (refer to Section 6.1 and Section 10.5.2 for additional information)
- Vital signs (as detailed in Section 6.1)
- Weight
- Urine or serum medically supervised pregnancy test with a minimum sensitivity of 25 mIU/mL for FCBP
- For female subjects only - menstrual status
- Hematology (as detailed in Section 6.1)
- Serum chemistry (as detailed in Section 6.1)
- Urinalysis: microalbumin, creatinine, microalbumin/creatinine ratio (morning void; central lab)
- 12-lead electrocardiogram (ECG) – read locally
- PK – refer to Section 6.8
- ADA – refer to Section 6.9
- Serum erythropoietin
- MRI for LIC (T2\* or R2, mg/g dw). The same MRI technique should be used within a subject throughout the study duration.
- MRI or abdominal ultrasound for spleen measurement, unless splenectomized (as detailed in Section 6.1)
- MRI for myocardial iron (T2\*; ms)
- Bone mineral density of total hip and lumbar spine by DXA scan (as detailed in Section 6.1)
- Serum ferritin
- CCI [REDACTED]
- CCI [REDACTED]
- HRU

